### Prior/Concomitant Therapy

- [24] Have received systemic nonbiologic therapy (including, but not limited to, oral psoralen plus ultraviolet A [PUVA] light therapy; cyclosporine; corticosteroids; methotrexate; oral retinoids; apremilast; tofacitinib; mycophenolate mofetil; thioguanine; hydroxyurea; sirolimus; tacrolimus; azathioprine; leflunomide; fumaric acid derivatives; or 1, 25 dihydroxy vitamin D3 and analogues) or phototherapy (including either oral and topical PUVA light therapy, ultraviolet B, excimer laser, or self treatment with tanning beds or therapeutic sunbathing) within 28 days prior to baseline.

#### [24a] GPP/EP ONLY:

- Methotrexate or oral retinoids will be permitted before and during the study if doses are not greater than that of baseline.
- Oral corticosteroids will be permitted before and during the study, if average daily doses are not greater than 10 mg/day of prednisone or its equivalent.
- Cyclosporine will be permitted until Week 2 (Visit 4), if daily doses are not greater than that of baseline.

- [25] Have received topical treatment (including, but not limited to, corticosteroids [mild or least potent topical steroids will be permitted for use limited to the face, axilla, or genitalia], crisaborole, anthralin, calcipotriene, topical vitamin D derivatives, retinoids, tazarotene, pimecrolimus, tacrolimus, emollients and other nonprescription topical products containing urea, >3% salicylic acid, alpha- or beta-hydroxyl acids, or medicated shampoos [for example those that contain >3% salicylic acid, corticosteroids, coal tar, or vitamin D3 analogues]) within 14 days prior to baseline.

#### [25a] GPP/EP ONLY:

- All topical treatment will be permitted before and during the study.

- [28] Have previous exposure to any biologic therapy targeting IL-12/23 (p40 subunit) or IL-23 (p19 subunit) or IL-17, either marketed or investigational.

#### [28a] GPP/EP ONLY:

- Previous exposure targeting IL-17 is permitted before the study, unless the patient received anti-IL-17 targeting biologics within 12 weeks prior to baseline.

### Other Exclusions

[38] Have a positive beta-D-glucan test at screening.

#### **4.5. Section 7.7: Concomitant Therapy**

All concomitant medications taken during the study must be recorded on the applicable Concomitant Medication electronic case report form (eCRF). All patients should maintain their usual medication regimens for concomitant conditions or diseases throughout the study unless those medications are specifically excluded in the protocol.

Patients taking concomitant medications should be on stable dosages at the time of baseline and should remain at stable dosages throughout the study unless changes need to be made because of AEs.

For patients with GPP or EP, methotrexate and oral retinoids will be permitted before and during the study if the patients have been using such medication before starting the study and if doses are not greater than that of baseline. Oral corticosteroids will be permitted before and during the study, if the patients have been using such medication before starting the study and if average daily doses are not greater than 10 mg/day of prednisone or its equivalent. Cyclosporine will be permitted until Week 2 (Visit 4), if the patients have been using such medication before starting the study and if daily doses are not greater than that of baseline. For methotrexate, oral retinoids, oral corticosteroids and cyclosporine, dose reductions are allowed but dose increases of these drugs are not allowed during the study. All topical treatment will be permitted before and during the study.

Additional systemic drugs are to be avoided during the study, unless required to treat AEs. If the need for concomitant medication arises for an AE or for appropriate medical management (including the limited use of therapeutic agents which, if used under treatment regimens other than for treating an AE or for appropriate medical management, might be considered psoriasis therapies), the investigator should base decisions on the patient and clinical factors. Other medications may be allowed if they are approved by the Sponsor or its designee.

Use of nonlive (killed, inactivated, or subunit) vaccinations are allowed for all patients; however, their efficacy with concomitant mirikizumab is unknown. Use of live, attenuated vaccines are prohibited.

Classes of therapies not permitted during the course of the study or permitted with use restrictions are specified in [Table AMAJ\(1\).2](#) (see also the Exclusion Criteria [[Section 6.2 of the protocol](#)]):

**Table AMAJ(1).2. Excluded Classes of Concomitant Medications or Classes with Restricted Use**

Drug Class	Allowed for Chronic Use	Allowed with Restrictions	Conditions for Allowed Use
Topical treatment for psoriasis or any other skin condition (including but not limited to, corticosteroids, crisaborole, anthralin, calcipotriene, topical vitamin D derivatives, retinoids, tazarotene, pimecrolimus, tacrolimus, emollients and other nonprescription topical products containing urea, >3% salicylic acid, alpha- or beta-hydroxyl acids)	N	N	Exception: For patients with GPP or EP, all topical treatments will be permitted. These topical medications should not be used within approximately 12 hours prior to study visits.
Topical treatment for psoriasis limited to face, axilla, or genitalia	N	Y	Mild or least potent topical steroids will be permitted for use limited to the face, axilla, and/or genitalia, as needed. These topical medications should not be used within approximately 24 hours prior to study visits.
Photochemotherapy (for example, PUVA)	N	N	
Phototherapy (for example, UVA, UVB, excimer laser)	N	N	
Biological immunomodulating agents (for example, alefacept, briakinumab, efalizumab, ixekizumab, secukinumab, etanercept, adalimumab, infliximab, certolizumab)	N	N	
Other systemic immunomodulating treatments (for example, MTX, cyclosporine A, corticosteroids, cyclophosphamide)	N	N	Exception: For patients with GPP or EP, methotrexate will be permitted before and during the study if doses are not greater than that of baseline, oral corticosteroids will be permitted before and during the study, if average daily doses are not greater than 10 mg/day of prednisone or its equivalent, and cyclosporine will be permitted until Week 2 (Visit 4), if daily doses are not greater than that of baseline. For these treatments, dose reductions are allowed but dose increases are not allowed during the study.

Drug Class	Allowed for Chronic Use	Allowed with Restrictions	Conditions for Allowed Use
*Systemic immunomodulating treatments ( corticosteroids only )	N	Y	Limited use of systemic corticosteroid ONLY as needed for limited, short-term medical management of TEAE may be considered. Such drug class might be considered psoriasis therapy if used under other regimens. Limited use during TEAE management is considered to not be consistent with psoriasis therapy.
Systemic psoriasis therapies ( for example, retinoids, fumarates, apremilast )	N	N	Exception: For patients with GPP or EP, oral retinoids will be permitted before and during the study if doses are not greater than that of baseline. For this treatment, dose reductions are allowed but dose increases are not allowed during the study.
Bacillus Calmette-Guerin (BCG) vaccinations or live virus vaccinations ( prohibited throughout the study and for 12 months or 12 weeks, respectively, after discontinuation of study drug ).	N	N	
Any investigational treatment	N	N	

Abbreviations: EP = erythrodermic psoriasis; GPP = generalized pustular psoriasis; MTX = methotrexate; N = No; PUVA = psoralen and ultraviolet A; TEAE = treatment-emergent adverse event; UVA = ultraviolet A; UVB = ultraviolet B; Y = Yes.

#### 4.6. Section 8.2: Discontinuation from the Study

In addition, patients who meet any one of the following criteria should be discontinued from the investigational product and enter the Post-Treatment Follow-Up Period, and discontinue from the study.

- If a patient has a confirmed diagnosis of PCP during the study, the patient must discontinue the study (protocol Section 9.4.3.2 in Section 4.7 of this addendum).

#### 4.7. Section 9: Study Assessments and Procedures

##### 9.1.4. Exploratory Efficacy Assessments for Patients at Sites in Japan

###### Assessment of Dermal Symptoms

Assessment of dermal symptoms, according to the Japanese Dermatological Association GPP revised criteria (Terui et al. [WWW]), will be performed only for patients with GPP. Skin symptoms are assessed by the score with the area of erythema (on a 0-3 scale), erythema with

pustules (on a 0-3 scale), and area of skin edema (on a 0-3). The total score will be assessed at visits indicated in the Schedule of Activities (Section 4.1 of this addendum).

### **Global Improvement Scores**

Global improvement scores will be collected for patients with GPP or EP from Week 2. Global improvement will be assessed in the 4 grades by comparing the psoriatic findings: (1) resolved, (2) improved, (3) unchanged, (4) worsened. The global improvement score is assessed based on the comparison of the psoriatic findings, sPGA, PASI score, and other evaluations with those at the baseline. The global improvement score will be assessed at visits indicated in the Schedule of Activities (Section 4.1 of this addendum).

#### **9.2.1. Serious Adverse Events**

When an in-hospital patient enters the study (GPP, EP), the investigator should consider their past experience of treatment of psoriasis to evaluate whether mirikizumab prolonged the hospital stay of a patient. Only if the investigator considers that mirikizumab truly prolonged the inpatient hospitalization, then worsening of the underlying condition of GPP or EP can be considered as an SAE.

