### 3. Rationale for Addendum

The following additions are being made to Protocol I6T-MC-AMAJ (AMAJ) for patients in Japan in order to conform with local requirements. This addendum is to be performed in Japan in addition to all procedures required by this protocol or any subsequent amendments to this protocol.

This addendum enables the inclusion of patients with generalized pustular psoriasis (GPP) and erythrodermic psoriasis (EP). These variants of psoriasis are relatively rare but can be more severe than chronic plaque psoriasis. GPP is characterized by multiple sterile pustules all over the body and may be accompanied by systemic symptoms including fever, chills, severe itching, dehydration, rapid pulse rate, exhaustion, anemia, weight loss, and muscle weakness. For this addendum, the eligibility criteria for GPP are set by the Japan Ministry of Health, Labour and Welfare (MHLW). EP is a particular inflammatory type of psoriasis that can affect the whole body. The reddening and shedding of the skin are often accompanied by severe itching and pain, heart rate increase, fluid loss, and fluctuating body temperature. For this addendum, the eligibility criteria for EP are based on the accepted current medical practice (Takigawa et al. 2010). Both psoriasis subtypes can sometimes be life-threatening without adequate treatment. The treatment options available for severe plaque psoriasis have been used in both subtypes, but often these subtypes are refractory to existing therapies. There are significant unmet medical needs for effective treatments for patients with GPP or EP.

Based on (1) postmarketing findings in Japanese patients with rheumatoid arthritis who were receiving anti-tumor necrosis factor (TNF) agents (Takeuchi et al. 2008; Koike et al. 2009), (2) recommendations set by the Japanese Dermatological Association for use of biologics in psoriasis (Ohtsuki et al. 2013), and (3) possible safety issues of Japanese patients with general autoimmune disease who received immunomodulators or immunosuppressants, the following additions are being made to Protocol AMAJ for patients in Japan:

- Chest radiography will be performed:
  - at Week 52
  - for subjects who discontinue the study early, if more than 12 weeks have elapsed since the previous study radiography was obtained. If medically indicated, this radiography may be performed even when 12 weeks have not elapsed since the previous study radiography

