### 5.1. Overall Design

Study I6T-MC-AMAJ is a Phase 3 multicenter, randomized, double-blind, placebo- and active-controlled, parallel group, multi-period study in adult patients with moderate-to-severe plaque psoriasis. Approximately 1443 patients will be randomized to treatment groups involving

different mirikizumab doses, placebo, or secukinumab. The study is comprised of 2 treatment periods (Induction, and Maintenance) which together lasts for up to 52 weeks, followed by a 12-week Post-Treatment Follow-Up period. The main protocol for Study AMAJ will enroll patients with plaque psoriasis (Cohort 1).

In parallel, the AMAJ(1) addendum will enroll Japanese patients who are diagnosed as GPP by the Japanese Dermatological Association or EP who have  $\geq 80\%$  body surface area (BSA) involvement (with inflammatory erythema) (Cohort 2). Approximately 8 patients with GPP and 8 patients with EP will be enrolled in Cohort 2 in Japan. During the Induction Period, GPP and EP patients will receive 250 mg mirikizumab subcutaneously (SC) at Weeks 0, 4, 8, and 12. During the Maintenance Period, starting at Week 16, GPP and EP patients will receive 250 mg mirikizumab every 8 weeks (Q8W) SC for up to a total of 52 weeks. Placebo control is not required for the GPP and EP patient arms because placebo-controlled studies are not ethical for patients with these severe conditions. The enrollment period of Cohort 2 will begin in parallel with the enrollment period of Cohort 1, but Cohort 2 enrollment may continue for a longer period of time if necessary to achieve the numbers planned for Cohort 2.

Figure AMAJ(1).1 illustrates the study design.

Abbreviations: EP = erythrodermic psoriasis; GPP = generalized pustular psoriasis;  
 LV = last study visit; miri = mirikizumab; Q4W = every 4 weeks; Q8W = every 8 weeks; V = visit; w = weeks; W = week.

\* Option to enter Study AMAH or to enter the Post-Treatment Follow-Up Period.

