Abbreviations: EP = erythrodermic psoriasis; GPP = generalized pustular psoriasis; PASI = Psoriasis Area and Severity Index; sPGA = static Physician's Global Assessment.

^a (Terui et al. [WWW]).

Table AMAJ.App.4. Description of Efficacy/Health Outcomes Analyses for Japan Addendum

Measure	Variable	Analysis Method	Population	Time Point and Period
Global Improvement Score	Global improvement score	Descriptive statistics for each grade based on observed	Japan Addendum Intent-to-Treat Population – Patients with GPP or EP	All scheduled visits in Induction and Maintenance Periods
GPP dermal symptom total score	GPP dermal symptom total score change from baseline	Descriptive statistics based on observed and mBOCF	Japan Addendum Intent-to-Treat Population – Patients with GPP	All scheduled visits in Induction and Maintenance Periods
PASI	PASI change from baseline	Descriptive statistics based on observed and mBOCF	Japan Addendum Intent-to-Treat Population – Patients with GPP or EP	All scheduled visits in Induction and Maintenance Periods
DLQI	DLQI total score change from baseline	Descriptive statistics based on observed and mBOCF	Japan Addendum Intent-to-Treat Population – Patients with GPP or EP	All scheduled visits in Induction and Maintenance Periods

Abbreviations: DLQI = Dermatology Life Quality Index; EP = erythrodermic psoriasis; GPP = generalized pustular psoriasis; mBOCF = modified baseline observation carried forward; PASI = Psoriasis Area and Severity Index.

App.2.4. Japan Addendum Safety Analyses

The following safety summaries will be provided for the Japan Addendum Safety Population – Patients with GPP or EP, for the Induction and Maintenance Periods:

- overview of adverse events (AEs)
- treatment-emergent adverse event (TEAE) by Preferred Terms (PTs)
- TEAE by PTs within System Organ Class
- TEAE maximum severity by PTs
- serious adverse event (SAE) by PTs
- AEs leading to treatment discontinuation
- listings of SAEs
- laboratory tests: box plot of change from baseline by visit
- vital signs: box plot of change from baseline by visit
- immunogenicity: incidence of antidrug antibodies

References

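### For GPP/EP patients already in hospital at entry, the addendum ties the seriousness of worsening disease to the investigator's view that mirikizumab lengthened the stay, so seriousness depends on causality

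*Protocol*

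**What the plan says.** Addendum Section 4.7, under Section 9.2.1 (Serious Adverse Events), opens "When an in-hospital patient enters the study (GPP, EP", so it applies to GPP and EP patients who are in-patients at entry. The investigator is to draw on earlier experience of treating psoriasis "to evaluate whether mirikizumab prolonged the hospital stay of a patient". The rule follows. Its condition reads "Only if the investigator considers that mirikizumab truly prolonged the inpatient hospitalization". Where that condition is met, the stated consequence is "then worsening of the underlying condition of GPP or EP can be considered as an SAE".

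Other parts of the documents bear on this:

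- **Size and design of Cohort 2.** Addendum Section 5.1 states: "Approximately 8 patients with GPP and 8 patients with EP will be enrolled in Cohort 2 in Japan". There is no placebo arm, and SAP App.2.2 assigns all these patients to mirikizumab.
- **Gravity of the diseases.** The addendum's rationale (Section 3) says: "Both psoriasis subtypes can sometimes be life-threatening without adequate treatment".
- **Relation to the main protocol.** The same section says: "This addendum is to be performed in Japan in addition to all procedures required by this protocol".
- **Planned output.** SAP App.2.4 lists "serious adverse event (SAE) by PTs" and SAE listings for Cohort 2. GPP and EP are reported separately (SAP App.2.2).

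**The concern.** Seriousness and relatedness are different judgements. Seriousness describes what happened to the patient, here whether the hospital stay became longer. Relatedness is an opinion about why. The addendum makes the first conditional on the second: a longer stay with worsening GPP or EP is not enough, because the investigator must also hold mirikizumab responsible.

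The screen works in one direction. If the drug fails and the disease progresses, the natural attribution is to the disease, and the event then loses its serious label. With no comparator in Cohort 2, the investigator has only past experience against which to judge what the drug did. At stake are expedited reporting of such events and the completeness of the SAE table and listing in a very small dataset that supports registration in Japan. A screen applied before the event is classified cannot be undone at analysis.

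**Working it through.** The documents give no figure to reproduce on this point. The check is mainly textual, with a short calculation for scale.

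**Step 1. What is tested.** Both sentences of addendum Section 9.2.1 ask whether mirikizumab lengthened the stay, not whether the stay was lengthened. Three cases for an in-patient whose GPP or EP worsens:

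| Stay longer than expected? | Attributed to mirikizumab? | May the worsening be called an SAE under the paragraph? |
|---|---|---|
| No | – | No |
| Yes | Yes | Yes |
| Yes | No | No |

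Rows two and three have the same outcome and differ only in attribution. This holds even if the paragraph is confined to the prolonged-hospitalisation criterion.

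**Step 2. Whether the SAP restores row three to the SAE outputs.** It does not. App.2.4 tabulates and lists events already classed as serious and adds no rule to recover others.

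**Step 3. Where row three still appears.**

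- SAP Section 6.8.2 has a preexisting condition that worsens after consent recorded as an adverse event.
- The treatment-emergent definition in Section 6.14.2 has no causality condition.
- App.2.4 plans treatment-emergent events by preferred term and by maximum severity, and events leading to discontinuation of treatment.
- The global improvement score has a worsened grade, and PASI and the GPP dermal score are also summarised (App.2.3).

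The efficacy scores are only a partial substitute. The global improvement score is summarised on observed data only. Under mBOCF (Section 6.3.3), a patient who stops for an adverse event has baseline carried forward, so worsening becomes zero change in that analysis. None of these records carries the seriousness label.

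**Step 4. Scale of one event.** With 8 patients per disease, one reclassified event moves the SAE rate from 0/8 = 0% to 1/8 = 12.5%. Exact (Clopper-Pearson) 95% intervals:

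- 0/8: upper limit 1 − 0.025^(1/8) = 36.9%, so 0 to 36.9%.
- 1/8: lower limit 1 − 0.975^(1/8) = 0.3%; upper limit, the 97.5% point of Beta(2, 7), = 52.7%.

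**Step 5. Illustration under assumptions that are not in the documents.** Let p be the true risk of serious worsening, c the share of such events attributed to mirikizumab, and suppose all 8 patients are in hospital at entry. The chance that at least one SAE is reported is 1 − (1 − pc)^8:

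| p | No causality condition (c = 1) | c = 0.5 | c = 0.25 | c = 0 |
|---|---|---|---|---|
| 10% | 57% | 34% | 18% | 0% |
| 20% | 83% | 57% | 34% | 0% |
| 30% | 94% | 73% | 46% | 0% |

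If only m of the 8 are in-patients and the others carry the same risk without the condition, the chance is 1 − (1 − pc)^m × (1 − p)^(8 − m). For p = 20% and c = 0.25:

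- m = 8: 1 − 0.95^8 = 34%
- m = 4: 1 − 0.95^4 × 0.8^4 = 1 − 0.8145 × 0.4096 = 67%
- m = 0: 1 − 0.8^8 = 83%, so the paragraph has no effect

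**The case against.** The strongest defence is that the paragraph is a clumsy but narrow aid. For someone already admitted, a prolonged stay needs an expected stay to compare with, and the investigator's experience supplies one. On this view the sentence only settles when an existing admission counts as prolonged.

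Three stronger readings are tempting and are not supported:

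- **A reader might infer that life-threatening or fatal worsening is not an SAE unless the drug is blamed.** That requires the paragraph to replace the main protocol's definition of an SAE. The main protocol's Section 9.2.1 was not available, the addendum applies on top of the main protocol, and it marks deletions by strikethrough; none is shown in this paragraph. The inference stays conditional. The sentence has no carve-out for such events, so the question is open.
- **A reader might infer that the events disappear.** They should not. Worsening is still to be recorded as an adverse event, summarised by term and severity, and reflected in the efficacy scores. What is lost is the serious label and what follows from it.
- **A reader might infer that the rule covers any hospitalised GPP or EP patient, or that the documents expect mirikizumab to worsen the disease.** It covers in-patients at entry only, and the rationale links the danger to inadequate treatment, not to the drug.

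It is also fair that the number of in-patients could be zero, that Cohort 2 is excluded from the analysis for global registrations, and that no formal inference is planned for it. A pooled figure of 1/16 = 6.25% would match no App.2.4 output, since GPP and EP are reported separately.

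The defence limits the reach of the point but does not remove it. Even on the narrow reading, the test is whether the drug lengthened the stay, so attribution still decides seriousness.

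**Conclusion.** The point holds in a limited form. For GPP and EP patients in hospital at entry, and at least for the prolonged-hospitalisation criterion, seriousness of worsening disease depends on the investigator's view of causality. Worsening with a longer stay that is attributed to the disease would be left out of SAE reporting and of the Cohort 2 SAE table and listing, while remaining a non-serious adverse event.

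The effect on fatal or life-threatening worsening cannot be settled without the main protocol's Section 9.2.1. The overall size is unknown because the number of in-patients at entry is not stated. One event is worth 12.5 percentage points in a group of 8; the probabilities in the illustration rest on assumed risks, attribution shares and in-patient numbers, and show direction only.

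**What to change.** Reword the Section 9.2.1 paragraph of the addendum in three respects:

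1. For a GPP or EP patient in hospital at entry, decide seriousness on outcome, that is, whether the stay was prolonged, regardless of cause. The investigator's experience may still inform what length of stay was expected.
2. Record the relationship to mirikizumab as a separate judgement.
3. State that the paragraph does not override the other seriousness criteria in the main protocol.

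If the sponsor wants to exempt expected disease progression from SAE reporting, that should be stated explicitly and should not depend on causality. Reporting the number of GPP and EP patients in hospital at entry would let readers judge how far the paragraph mattered.

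The cost is one addendum paragraph, notification of the Japanese sites, and possibly a few more SAE reports. The SAP outputs need no change.
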